#### **4.1 Data Analysis**

The objectives of this study are outlined in Section 1.3. For purposes of this study, economic outcomes of interest include the peri-operative time, intra-operative time (OR efficiency), and sterilization times as quantitative values. These outcomes will be subsequently used in comparative cost analyses. The secondary objectives are to assess the accuracy of mechanical axis alignment and posterior tibial slope after total knee replacement, additional operative parameters, and adverse events.

Descriptive statistics, specifically means will be used to summarize the peri-operative, intra-operative and sterilization time data.

The primary objective will be met by comparing mean values of each of the time-saving parameters. The null hypotheses of no differences in mean values between re-usable and single-use devices will be tested using separate t-tests for two independent groups for each endpoint. A p-value of less than 0.05 will be considered significant for each endpoint. Endpoints with statistically significant differences are expected to contribute to expected cost differences to be determined in subsequent analyses.

Descriptive analyses as well as similar two-sample comparisons will be used to evaluate secondary measures.

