### **1.2 Study Treatment**

The GMK single-use (Efficiency) instruments are made of medical-grade composite technopolymers that give high fatigue and abrasion resistance in addition to form versatility. The single-use instruments are shipped from the manufacturer in pre-sterilized packaging, eliminating the need to use the hospital Central-Sterile processing equipment. The reproducible sterility may potentially reduce the infection risk.

---

 Losina E, *et al.* Cost-effectiveness of Total Knee Arthroplasty in the United States: Patient Risk and Hospital Volume. *Arch Intern Med* (2009); 169(2):1113-1122.

 Mont MA, *et al.* Single-Use Instruments, Cutting Blocks, and Trials Increase Efficiency in the Operating Room During Total Knee Arthroplasty: A Prospective Comparison of Navigated and Non-Navigated Cases. *J Arthroplasty* (2013); 28(7):1135-1140.

 Siegel Gw, *et al.* Cost Analysis and Surgical Site Infection Rates in Total Knee Arthroplasty Comparing Traditional vs. Single-Use Instrumentation. *J Arthroplasty* (2015); 30: 2271-2274

 Lachiewicz, PF, Henderson, RA: Patient-specific Instruments for Total Knee Arthroplasty. *J Am Acad Orthop Surg*, 2013; 21:513-518.

MyKnee® patient-specific cutting blocks allow the surgeon to realize his pre-operative 3D planning, based on CT or MRI images of the patient's knee. The blocks are created based on the individual patient's anatomy, his/her mechanical axis, and the surgeon's preferred reconstruction goals. The innovative concept combines the following features giving potential benefits to both the surgeon and the patient:

- Accurate bony cuts and therefore implant positioning
- No intramedullary canal violation
- Up to 60% reduction of surgical steps for bone resection and related time
- Up to 66% reduction of time and cost in washing, assembling and sterilization procedures
- Interactive 3D web planning

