### **STUDY DESIGN**

The study is a multi-center, prospective, randomized study comparing surgical and economic parameters of Total Knee Replacement performed with single-use Efficiency instruments with patient-specific technique (MyKnee®) versus traditional metal instruments with conventional surgical technique. The objective is to evaluate the impact of single-use instrumentation versus traditional metal instruments in reducing overall surgical costs and improving mechanical axis alignment. The timing of routine surgical phases will be measured, including the pre-operative preparation time, intra-operative phase, OR clean-up time and sterilization phase in 300 adult patients undergoing total knee replacement. AP and lateral x-rays will be utilized to assess the implant's mechanical axis alignment and tibial slope after discharge to the completion of the 6 week visit. Additionally, other parameters will be recorded including blood loss, post-op day 1 hemoglobin drop, adverse events, number of trays sent to sterilization, and total waste weight at the end of each procedure, considering separately those recyclable and those not recyclable. To ensure that the minimum of 300 patients is met, 342 patients will be randomized into two treatment cohorts in a 2:1 ratio.

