#### **Group A: Single-Use Efficiency Instruments with Patient Specific Technique (Efficiency/MyKnee®)**

Patients randomized to Group A will undergo surgery utilizing single-use Efficiency Instruments with patient-specific technique (MyKnee® patient-matched cutting blocks)

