#### **Group B: Traditional Metal Instruments with Conventional Surgical Technique (Conventional TKA)**

Patients randomized to Group B will undergo conventional surgical technique utilizing traditional metal instrumentation and traditional cutting blocks (Metal)

Additional demographic information will be collected to describe the study population and to document whether the two treatment groups are clinically comparable. Data collected will include: age, gender, BMI, race/ethnicity, smoking history, and employment status, in addition to pre-operative knee history/diagnosis and degree of pre-operative knee malalignment and Kellgren-Lawrence grade.

## 3

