### **BENEFIT / RISK PROFILE**

#### 5.1 Potential Benefits

Results of this study will be helpful in evaluating the impact of single-use instrumentation versus traditional metal instruments on overall surgical cost reduction and improving mechanical axis alignment improvement when using patient-matched cutting blocks. The study will provide the initial data to understand the health economic impact of the Efficiency single-use instrumentation when using MyKnee® patient-matched cutting blocks.

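### The two groups differ in both instruments and technique, but the Section 2 objective, the 4.1 null hypotheses and the sample-size heading describe a single-use device effect that this design cannot isolate

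*Combined protocol and SAP*

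**What the plan says.** All references are to the combined protocol and SAP.

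**The arms.** Section 2 assigns Group A to single-use Efficiency instruments with MyKnee patient-matched blocks, and Group B to metal instruments with traditional blocks and conventional technique. There is no third arm.

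**Places that name the package.** The title does, as do the opening sentence of Section 2 and Section 1.3, where the primary objective compares the two procedures. Section 4.1 refers the reader to Section 1.3 for the objectives.

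**Places that name only the device.**
- The objective sentence in Section 2 is to "evaluate the impact of single-use instrumentation versus traditional metal instruments in reducing overall surgical costs and improving mechanical axis alignment".
- Section 4.1 tests "The null hypotheses of no differences in mean values between re-usable and single-use devices".
- The heading of the sample-size table in 4.2 presents a main effect of device type, and the effect sizes come from a published single-use versus re-usable comparison, pooled over navigation.

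**A mixed place.** Section 5.1 speaks of "the impact of single-use instrumentation versus traditional metal instruments on overall surgical cost reduction", but the same sentence goes on to mention the patient-matched blocks, and the next sentence names both components.

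**What is expected of the blocks.** Among the potential benefits of MyKnee, Section 1.2 lists "Up to 60% reduction of surgical steps for bone resection and related time" and "Up to 66% reduction of time and cost in washing, assembling and sterilization procedures", as well as more accurate cuts and implant positioning.

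**The concern.** The analysis tests one thing and three passages describe another. If a time endpoint is significant, the null as worded in 4.1 invites the conclusion that single-use instruments made the difference. The patients behind that result were also assigned custom cutting blocks and the CT- or MRI-based planning that goes with them. Section 4.1 then carries significant endpoints into the cost comparison, so the label would travel with them. Alignment shows the problem most clearly: Section 2 frames it as an effect of single-use instruments, while Section 1.2 gives accurate positioning as a benefit of the blocks.

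Section 1.3 expects surgeons, facilities and payors to use the results when choosing instrumentation. The claim they read should match what was randomized.

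**Working it through.** **1. The plan's own sample size.** Inputs from 4.2 for set-up time, the limiting endpoint: d = 2.985, SD = 8.66, effect size 0.345, 2:1 allocation, 80% power. Alpha is 0.05 per endpoint (4.1), taken as two-sided because the plan does not say.

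Controls = (1 + 1/2) × (1.960 + 0.842)² × (SD/d)² = 1.5 × 7.849 × (8.66/2.985)² = 99.1, rounded up to 100. Total = 3 × 100 = 300, and 300 × 1.14 = 342. The t-based calculation gives 298.7. The stated figure reproduces. Power at 228:114 is about 85%.

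**2. What the contrast estimates.** Let D be the instrument effect and T the technique effect, with any interaction absorbed into T. Then mean(A) − mean(B) estimates D + T. That is one estimable quantity for two unknowns, and no arm supplies a second equation. Section 1.3 foresees Group A cases in which MyKnee is aborted for standard blocks. Those cases are not randomized, so they do not separate D from T.

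**3. Range of the instrument share, D/(D + T).** Take an observed total of 0.245 SD.
- D = 0.345, T = −0.1: share = 0.345/0.245 = 141%.
- D = −0.1, T = 0.345: share = −0.1/0.245 = −41%.

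Both fit the same data, so the share is not confined to the interval from 0 to 100%.

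**4. Do the components act on the same endpoints?**

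| Potential benefit of MyKnee (1.2) | Endpoint in the trial |
|---|---|
| Fewer resection steps, less related time | Femoral and tibial resection times (3.3) |
| Less washing, assembly and sterilization time and cost | Cleaning and sterilization phase times (3.3); sterilization costs (1.3) |
| Accurate cuts and positioning | Mechanical axis and tibial slope (1.3, 3.3) |

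The percentages in Section 1.2 cannot be converted into T for the planned tests. They are upper limits on resection and processing, whereas the table in 4.2 covers set-up, clean-up, their combination and surgical episode time, in minutes.

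**5. Illustration with an assumed T.** The values of T below are assumptions, not figures from the documents. At 228:114 the standard error in SD units is √(1/114 + 1/228) = 0.1147. Write Φ for the standard normal distribution function.

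If D = 0, the probability of rejecting the null as worded is Φ(T/0.1147 − 1.96) + Φ(−T/0.1147 − 1.96):

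| Assumed T (SD) | Probability of rejection |
|---|---|
| 0 | 5.0% |
| 0.1 | 14.1% |
| 0.2 | 41.4% |
| 0.3 | 74.4% |
| 0.345 | 85.3% |

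If D = 0.345 and T = −0.1, −0.2 or −0.3, the power to reject in favour of Group A is Φ((D + T)/0.1147 − 1.96). It falls from 85% to 57%, 24% or 6%. Either a positive or a null result could be credited to the wrong component.

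**The case against.** The strongest reply is that *single-use* is an arm label. Section 3.2.2 adds MyKnee in brackets, and 4.2 writes the full package and then shortens it when giving the allocation. With two arms and independent-group t-tests, the null can be computed only as Group A against Group B, and 4.1 defers to Section 1.3, which is worded correctly. Section 4.2 also calls its effect sizes approximate and gives uncertainty about them as one reason for the 14% increase.

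Much of this stands. It answers several stronger readings that a reader might infer:

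- *The trial cannot test its stated objective.* That is true of the objective sentence in Section 2, not of the title or Section 1.3. The package comparison is testable as randomized.
- *The documents show that the blocks alone cut time by 60% or 66%.* Section 1.2 presents these as potential, up-to figures, and does not say which instruments the blocks were used with.
- *Section 5.1 makes a device-only claim.* Read to the end, it mixes both framings.
- *The sponsor is committed to a device-only conclusion.* No passage says so.

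The label argument does not cover everything. The Section 2 sentence attributes an alignment improvement to single-use instruments, and the table heading calls the contrast a main effect of device type. Neither is a harmless abbreviation when the second component is expected to act on the same outcomes. The 14% increase is not explained by reference to MyKnee.

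**Conclusion.** The point holds as an inconsistency about what is being estimated, of low severity. The design supports a conclusion about the package. It does not support the device-only effect named in the Section 2 objective, the 4.1 nulls and the sample-size heading, and a conclusion taken from those words would be misattributed.

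The size cannot be fixed from the documents, because they give no block-only effect on the scale of the planned tests. The rejection rates of 14% to 85% rest on assumed technique effects of 0.1 to 0.345 SD with no instrument effect; they show how the error would arise and do not predict it. The non-identifiability itself needs no numerical assumption, since it follows from the two arms.

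A reader might also infer that the tests or the sample size are invalid. They are not: N = 300 reproduces, and the t-tests are valid for the package. What remains open is whether a single-use-only effect size suits the package, which the plan does not discuss.

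**What to change.** 1. Restate the Section 2 objective and the 4.1 null hypotheses as *Efficiency instruments with MyKnee versus metal instruments with conventional technique*.
2. Use the same wording throughout 5.1 and in the heading of the sample-size table.
3. Add to 4.1 that differences in time, cost and alignment will be concluded for the package and not for either component alone.
4. Note in 4.2 that the effect sizes come from a single-use-only comparison and serve as a proxy for the package.

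This changes wording only. Arms, randomization, data collection, tests and N = 342 stay as they are. The cost is a narrower claim for the single-use instruments.

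If the sponsor wants the instrument effect itself, a different design is needed. At 0.345 SD, 80% power and two-sided 0.05 (normal approximation, no multiplicity adjustment), a direct 1:1 contrast needs 2 × 7.849/0.345² = 131.9, so 132 per arm. That is 3 × 132 = 396 for three arms, or about 2 × 132 = 264 in total for a 2×2 factorial main effect if there is no interaction. Correcting the wording does not require this.

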#### Visit 1: Baseline (-1 to -90 days prior to surgery)

The baseline visit will occur to screen subjects, confirm study eligibility, complete the informed consent process, and enroll and randomize the subject.

- Informed consent
- Randomize patients meeting inclusion/exclusion criteria
- Collect demographics data, pre-operative knee history/diagnosis and employment status
- Visual Analog Scale (VAS) for knee pain
- Long standing AP and lateral x-rays to assess pre-operative mechanical axis alignment and posterior tibial slope. X-rays obtained within 6 months prior to surgery are acceptable for the baseline visit. The investigator may repeat x-rays if needed for clinical or imaging quality reasons.
- Complete CT scan or MRI for pre-operative planning and selection of cutting blocks (Group A Only)

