#### **4.2 Sample Size Analysis**

Sample size for this study was determined on the basis of device group differences observed in the Mont et al 2013 study for four (related) but important health care utilization endpoints. The table below summarizes the data in Table 2 of Mont et al, but also provides a summary of the comparisons between single-use and re-usable pooling over whether or not navigation was employed. These data were used to approximate the expected effect size (standardized mean difference) comparing between single-use vs re-useable instruments. The sample sizes required for a two sample t-test to obtain 80%, 85%, and 90% power as a function of the observed pooled effect sizes were determined. The effect sizes were derived from the reported mean differences and p-values. The maximum sample size per group required to achieve at least 80% statistical power to reject the null hypothesis of equal group mean was determined across the four outcomes summarized in Table 2. For the 2:1 allocation between the single-use Efficiency instruments with MyKnee versus traditional metal instruments, this sample size was 200:100 or total N=300. This value was increased by 14% to N=342 to account for uncertainty in the estimated effect sizes, to account and to allow for additional analyses of economic outcomes. Therefore, 228 and 114 patients will be randomly allocated into single-use Efficiency instruments and traditional metal instruments arms respectively.

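### Section 4.1 analyses every endpoint without adjusting for site or baseline predictors that are already known, which costs precision but does not bias the comparison

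*Combined protocol and SAP*

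**What the plan says.** Section 4.1 states that the primary null hypotheses "will be tested using separate t-tests for two independent groups for each endpoint", and sets the criterion: "A p-value of less than 0.05 will be considered significant for each endpoint". For the rest it says "Descriptive analyses as well as similar two-sample comparisons will be used to evaluate secondary measures". Section 4 names no covariate, regression model or site term.

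The sample size matches that choice. Section 4.2 computes "The sample sizes required for a two sample t-test to obtain 80%, 85%, and 90% power", takes the largest N needed across four outcomes for 80% power (300, at 200:100), and raises it by 14% to 342 (228:114).

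Three other sections matter here:

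- Section 3.2.2: block randomization is run separately at each site.
- Section 2, under Group B: age, gender and BMI are recorded, as is the "degree of pre-operative knee malalignment and Kellgren-Lawrence grade". The stated purpose is to describe the sample and check that the arms are comparable.
- Section 3.4, Visit 1, requires "Long standing AP and lateral x-rays to assess pre-operative mechanical axis alignment and posterior tibial slope". Section 3.3 requires these films for every subject, before surgery and at 6 weeks.

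**The concern.** Randomization is stratified by site but the analysis ignores site. Any difference between sites in room set-up, staffing or sterilization practice therefore stays in the error term of the t-test, although the design has balanced it between arms. Likewise, patient features that plausibly affect time in the operating room, blood loss and alignment error are measured but not used to reduce residual variance.

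What is at stake is the width of the confidence intervals. The trial is meant to yield minutes saved, which then feed a cost calculation, so a tighter interval improves the main product directly. Section 4 allows post-hoc analyses, but a covariate set chosen after the data are seen is less credible than one fixed in advance.

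**Working it through.** **Inputs.** From the table in Section 4.2: set-up time, difference 2.985, SD 8.66, effect size 0.345; surgical episode time, difference 5.893, SD 16.79, effect size 0.351. Allocation is 2:1. Alpha is 0.05 per endpoint. Sidedness is not stated. It is taken as two-sided because Section 4.1 tests "The null hypotheses of no differences in mean values between re-usable and single-use devices", and two-sided testing reproduces the plan's N. R² is an assumption.

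**1. The plan's own figure.** For set-up time, n(control) = (1 + 1/2)(1.960 + 0.842)² / (2.985/8.66)² = 1.5 × 7.849 / 0.1188 = 99.1, rounded up to 100. This gives 200:100, total 300, as stated. 300 × 1.14 = 342, as stated.

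**2. Unadjusted power at 342.** The noncentrality is effect size / √(1/228 + 1/114) = effect size / 0.1147, with 340 degrees of freedom. Set-up time: 0.345/0.1147 = 3.01, power 85.1%. Episode time: 0.351/0.1147 = 3.06, power 86.2%.

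**3. Effect of adjustment on episode time.** A linear model multiplies the residual SD by about √(1 − R²), so the effect size becomes 0.351/√(1 − R²) and 342 patients act like 342/(1 − R²).

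| Assumed R² | √(1 − R²) | SE lower by | Effect size | Power at 342 | Equivalent N |
|---|---|---|---|---|---|
| 0 | 1.000 | 0 | 0.351 | 86.2% | 342 |
| 0.05 | 0.975 | 2.5% | 0.360 | 87.9% | 360 |
| 0.10 | 0.949 | 5.1% | 0.370 | 89.6% | 380 |
| 0.20 | 0.894 | 10.6% | 0.392 | 92.7% | 428 |

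In minutes, the SE of the episode-time difference goes from 16.79 × 0.1147 = 1.93 to 1.72 at R² = 0.20.

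**4. Why a setting term deserves attention.** The combined SDs in the table are close to averages of the two navigation-stratum SDs: (6.82 + 10.49)/2 = 8.66 and (14.58 + 18.98)/2 = 16.78. They leave out the gap between strata. For episode time the stratum means are (100.58 + 97.11)/2 = 98.8 and (128.51 + 119.61)/2 = 124.1, about 25.2 minutes apart. With 191 and 197 patients, the between-stratum variance is (191/388)(197/388)(25.2)² ≈ 159. The total SD is then √(16.79² + 159) ≈ 21.0, and strata explain 159/441 ≈ 36% of variance. A t-test that pooled over a gap of that size would work with effect size 5.893/21.0 = 0.281 and have about 63% power at 300 and 68% at 342. The strata are navigation, not site, so this illustrates how much a setting can matter and does not estimate site differences in this trial. The same calculation gives about 2% for set-up time and 13% for clean-up.

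**5. Which endpoints can gain from which terms.** Section 3.3 lists three preparation and clean-up times, seven sterilization times and four intra-operative items. BMI, age, sex and deformity plausibly bear on the intra-operative items, blood loss and alignment. Nothing in the documents suggests that they bear on how long staff take to lay out, collect or sterilize instruments. For those times, site is the plausible predictor.

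**The case against.** The strongest reply is that nothing here is wrong. The unadjusted t-test is valid under randomization, Section 4.2 sized the trial for that test, and analysis and sample size agree. That stands in full. A reader might infer that the unadjusted comparison is biased or its type I error inflated, but the documents do not support this.

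A reader might also infer that the trial has barely 80% power, so that adjustment is its only source of margin. Section 4.2 already adds 14% for uncertain effect sizes, and at 342 unadjusted power is 85–86% for the two hardest outcomes.

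It is tempting to quote the power gain for set-up time, because that outcome drives N. The arithmetic can be done, but there is no reason to expect patient covariates to explain set-up time, so their R² there may be near zero.

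A reader might say that pre-operative slope is ignored altogether. That is too strong: Section 3.3 measures accuracy against the surgeon's intended position, which for slope is usually the patient's own slope restored, so baseline slope already enters through the target.

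Two further points limit the gain. The R² range has no source in the documents. Eligibility also narrows the main predictors: BMI is capped at 40, and deformity beyond 15 degrees is excluded.

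Adjusting for the operating surgeon is also tempting, but the documents do not list surgeon among the data collected. Knee pain on the VAS is collected with no stated analysis; that is a separate matter from adjustment.

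**Conclusion.** The point holds as a free improvement in precision. It is not an error of validity. Every planned comparison is unadjusted, the randomization stratum is left out, and usable baseline predictors are collected in both arms.

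If the added terms explain 5–20% of within-arm variance, standard errors fall by 2.5–10.6% and power for surgical episode time at 342 goes from about 86% to 88–93%. These figures rest on the plan's own effect size and SD, two-sided testing, all 342 patients contributing, and the assumed R². The gain from site could be larger or negligible, because the documents say nothing about how much sites differ. For set-up, clean-up and sterilization times, any gain should be expected from site alone.

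**What to change.** In Section 4.1, make the main analysis of each continuous endpoint a pre-specified linear model with arm and site, and add:

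- **Intra-operative times and blood loss:** BMI, age, sex and absolute pre-operative mechanical-axis deviation.
- **Alignment error:** pre-operative axis deviation.
- **Slope error:** pre-operative slope.
- **Set-up, clean-up and sterilization times:** no patient covariates.

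Report the adjusted mean difference with a robust 95% confidence interval, and keep the two-sample t-test as a sensitivity analysis. Fix the covariate list before any outcome data are examined.

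The cost is SAP wording. Site is known from the randomization and the covariates are already collected. The model uses one degree of freedom for each site beyond the first (the number of sites is not given) and at most four for patient covariates. The sample size need not change.

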#### **Primary Objective:**

- To compare the time-saving parameters associated with the two procedures with respect to parameters such as OR preparation time, intra-operative time (OR efficiency), OR clean-up time and sterilization costs.

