### 3.3 *Evaluation Parameters*

### Time of Operative Phases

The time of the following pre-operative, operative and sterilization phases will be recorded (hh:mm:ss):

1. Surgery Room Preparation and Clean-up Phase
  - a. Instrument preparation for surgery from stock to Operative Room (OR)
  - b. Surgical table preparation
  - c. Instrument collection after surgery for sterilization
2. Intra-operative Phase
  - a. Patient OR time
  - b. Skin-to-skin time
  - c. Femoral and tibial resection times
  - d. Tourniquet time
3. Sterilization Phase
  - a. Instrument transportation to the sterilization unit
  - b. Instrument reception
  - c. Instrument cleaning before sterilization
  - d. Instrument decontamination before sterilization
  - e. Instrument sterilization
  - f. Instrument collection after sterilization
  - g. Instrument transportation to stock

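### The primary objective is a set of time comparisons, each tested at an uncorrected 0.05, so its familywise error exceeds 5%; the family and the success rule are not fixed

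*Combined protocol and SAP*

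**What the plan says.** Section 4.1 (Data Analysis) sets the rule: "The primary objective will be met by comparing mean values of each of the time-saving parameters". The null hypotheses "will be tested using separate t-tests for two independent groups for each endpoint", and "A p-value of less than 0.05 will be considered significant for each endpoint". Results are then carried forward: "Endpoints with statistically significant differences are expected to contribute to expected cost differences to be determined in subsequent analyses".

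The set of endpoints is described in four ways.

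- The Primary Objective gives four items, "OR preparation time, intra-operative time (OR efficiency), OR clean-up time and sterilization costs", introduced as examples.
- Section 4.1 names three groups of economic outcomes: peri-operative, intra-operative and sterilization times.
- Section 3.3 (Time of Operative Phases) says "The time of the following pre-operative, operative and sterilization phases will be recorded" and lists 3 + 4 + 7 = 14 items, or 15 if femoral and tibial resection are counted separately.
- Section 4.2 bases the sample size on "four (related) but important health care utilization endpoints" taken from a cited study: set-up, clean-up, their combination and surgical episode time.

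Section 4.2 takes the largest N over those four outcomes (300) and adds 14% to reach 342. The reasons it gives are effect-size uncertainty and additional economic analyses, not multiplicity.

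**The concern.** A 5% error rate per endpoint does not give 5% for an objective made up of several endpoints. Because the plan does not say which comparison, or how many, must succeed, any phase that reaches p<0.05 can be reported as a time saving under the primary objective. The choice of which result to lead with could be made after the data are seen.

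The cost analysis adds a second effect. Selecting phases by p-value lets chance findings into the cost estimate and tends to overstate the difference. Section 1.3 says the data are meant to help surgeons, facilities and payors choose instrumentation, so the reported saving is what would be used.

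**Working it through.** **1. Was an allowance for multiplicity built into N?** The inputs are in the Section 4.2 table. For set-up time the difference is 2.985 and the SD 8.66, so the effect size is 2.985/8.66 = 0.345. With 2:1 allocation and a two-sided test,

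n(control) = (1 + 1/2) × (1.960 + 0.842)² / 0.345² ≈ 99, rounded up to 100.

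That gives 100 + 200 = 300, the plan's figure (298.7 by the t-based solution). A one-sided test would give 237, which does not match. Then 300 × 1.14 = 342. The plan therefore used an uncorrected two-sided 0.05 for each endpoint.

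**2. Familywise error if no endpoint differs.** For m independent tests, the chance of at least one p<0.05 is 1 − 0.95^m. Counting only errors in the time-saving direction, it is 1 − 0.975^m.

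- m = 3: 14.3% (7.3% in the time-saving direction)
- m = 4: 18.5% (9.6%)
- m = 14: 51.2% (29.8%)

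The timings will be correlated, but the documents give no correlations. The values below are assumptions, simulated with equally correlated normal statistics (400,000 draws).

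| Correlation | m = 4, any p<0.05 | m = 4, false saving | m = 14, any p<0.05 | m = 14, false saving |
|---|---|---|---|---|
| 0.5 | 15.5% | 7.8% | 34.7% | 17.4% |
| 0.7 | 13.0% | 6.5% | 24.8% | 12.4% |
| 0.9 | 9.4% | 4.6% | 14.2% | 7.1% |

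The reference for the false-saving columns is 2.5%, which is what one two-sided 0.05 test allows in that direction.

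**3. The four sample-size endpoints.** Combined is the sum of set-up and clean-up (36.61 + 16.43 = 53.04; 39.00 + 24.96 = 63.96), so these four are not independent. The table's SDs imply a set-up/clean-up correlation of (14.63² − 8.66² − 9.72²) / (2 × 8.66 × 9.72) = 0.26. This is rough, because the SDs were back-calculated from p-values. With that structure and a common correlation of 0.27, the rates are 14.7% for any p<0.05 and 7.3% for a false saving.

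**4. If the seven sterilization times truly differ.** Seven true nulls remain. The rates are 1 − 0.95⁷ = 30.2% and 1 − 0.975⁷ = 16.2% if independent, and 17.8% and 8.9% at correlation 0.7.

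**5. What a correction costs.** Power at 228:114 for effect sizes 0.460 (Combined), 0.386 (clean-up), 0.351 (surgical episode) and 0.345 (set-up):

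- Uncorrected 0.05: 98%, 92%, 86%, 85%.
- Plain Bonferroni over four (0.0125): 93%, 80%, 71%, 69%.
- Holm over four, all four effects real, correlation 0 to 0.7 (simulated): 95–97%, 87–90%, 81–84%, 80–82%.

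Two limits apply to the Holm figures. If only set-up differed, Holm would give about 69%, the Bonferroni value. If only 300 patients were analysed (200:100), Holm power for set-up would be about 74–76%, against 80% uncorrected.

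**The case against.** The strongest reply is that the plan openly declares inference endpoint by endpoint, states no rule that any one significant result wins, and calls its results initial data (Section 5.1). That is a fair description, but the same text says the primary objective is met through these tests and sends the significant ones into the cost analysis. The lack of a success rule is part of the problem, not an answer to it.

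Three objections to the size of the error do stand.

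- A reader might infer that the plan has 14 primary endpoints. Section 3.3 only says those times are recorded; other sections name three groups or four items. The documents support an undefined family, not a family of 14.
- A reader might infer a one-in-two chance of a false claim of time saving. The 51% needs 14 independent tests and no true difference anywhere, and it counts false findings in both directions. Section 1.2 says the single-use instruments arrive pre-sterilized and bypass hospital sterile processing, so the seven sterilization steps are the least plausible nulls. Patient OR, skin-to-skin and tourniquet times overlap, so independence is unrealistic too.
- For a family of three or four related endpoints, the false-saving rate is about 4% to 10%. That is above the nominal 2.5%, but modest.

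A fixed testing order is a possible remedy, but running it over the four sample-size endpoints has drawbacks. Combined and surgical episode time are not listed under those names in Section 3.3, sterilization would drop out of the primary objective, and set-up in last place would have only about 66% to 77% power at correlations 0 to 0.7.

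**Conclusion.** The point holds. Following Section 4.1 as written gives a familywise error above 5% for the primary objective, and neither N = 300 nor the increase to 342 allows for it. If nothing differs, the chance of at least one p<0.05 is about 9% to 18.5% for four endpoints and 14% to 51% for 14. The chance of at least one false time-saving claim is about 5% to 10% and 7% to 30%.

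These ranges rest on assumed correlations from 0.9 to 0, on a family size the plan leaves open, and on no true difference anywhere. The last makes them upper-end figures. The documents do not support a single headline rate, nor a conclusion that the sample size must rise.

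**What to change.** Change Section 4.1 as follows.

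1. Define a short primary family from times recorded in Section 3.3: one total each for OR preparation, intra-operative time (for example patient OR time), clean-up and sterilization.
2. Test the four totals with Holm at a two-sided familywise level of 0.05, and state what counts as meeting the primary objective.
3. Report the individual phase times with 95% intervals and no significance claim.
4. Base the cost analysis on all the pre-specified totals, not on those reaching p<0.05.

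The cost is SAP wording, the definition of four totals, some power on single endpoints, and loss of confirmatory status for individual phases. With the plan's four effect sizes at 228:114, set-up goes from 85% to about 80–82% and Combined from 98% to about 95–97%. The stated 80% is kept and N does not change, provided close to all 342 patients contribute timings and the other effects are also real. The new totals are not the cited study's outcomes, so their effect sizes remain assumptions; Section 4.2 gives none for sterilization.
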